## Clinical Investigational Plan

### 5.0 DEVICE UNDER INVESTIGATION AND CONTROL/COMPARATORS (IF APPLICABLE)

#### 5.1 DEVICE DESCRIPTION

Infinity DBS system:

In this study, commercially available St. Jude Medical (SJM) Infinity DBS system components will be used. This neurostimulation system is designed to deliver electrical stimulation to targets in the brain. The neurostimulation system includes the following primary components:

- Implantable pulse generator (IPG)
- Leads
- Extensions
- Clinician programmer
- Patient controller

The IPG connects to the implanted extensions, which connect to the leads implanted in the brain. The IPG delivers electrical pulses through the extensions and leads to electrodes at a selected target in the brain in order to provide therapeutic stimulation. The patient magnet can turn the IPG on and off, if the physician enabled this functionality. Physicians use the clinician programmer to create and modify a program for a patient. Patients use the patient controller to control their prescribed programs. Components of the Infinity DBS system and model numbers are included in Appendix D.

##### Infinity Implantable Pulse Generator

This IPG is an electronic device designed to be connected to one or two extensions. It is powered by a hermetically sealed battery within a titanium case and uses microelectronic circuitry to generate constant-current electrical stimulation. The IPG is conductive on all sides, which allows the IPG case (also called a “can”) to be used as an anode for monopolar stimulation. The IPG communicates wirelessly with system programmers and controllers, and IPGs are available in small and large sizes to accommodate different power needs. The IPG can receive software upgrades after implantation to provide patients with additional features as approved by the respective regulatory agencies. To upgrade features on the IPG, a system programmer is needed.

##### Leads

St. Jude Medical DBS leads are designed for introduction into the brain using standard stereotactic neurosurgical techniques. Leads feature electrodes on a stiff distal end with an inactive lead tip. The proximal end of the lead contains contact bands that correspond with each of the distal electrodes and an inactive band that functions as a contact for a setscrew when connecting to a compatible extension. Additionally, the leads have colored bands that can help during implantation to differentiate between the right and left sides of the body. Two types of leads are available: 4 channel and 8 channel. The 4-channel leads contain cylindrical electrodes that provide stimulation in all directions around the lead. The 8-channel leads contain cylindrical and segmented electrodes. The segmented electrodes can be

## Clinical Investigational Plan

activated independently to focus stimulation in one direction to help exclusively target desired neurological structures.

### Extensions

St. Jude Medical DBS extensions are designed to connect the lead to the IPG. One end of the extension is designed to receive the proximal end of the lead, and the opposite end of the extension is designed for insertion and connection with the IPG.

### Clinician Programmer

The Clinician Programmer Application is a software application running on an iPad which is used by a clinician to wirelessly connect to Infinity IPGs to establish or modify a patient's stimulation prescription.

### Patient Controller

The Patient Controller is a component of the Infinity system. It is an off-the-shelf touch screen device (iPod Touch) with SJM-designed mobile Application Software.

## 5.2 DEVICE HANDLING AND STORAGE

Only regulatory approved and commercially available shelf-stock will be used within commercially approved indications for the investigation. No specific device traceability is required.

[figure not shown]

## Clinical Investigational Plan

### 6.0 PROCEDURES

#### 6.1 STUDY FLOW CHART

**Subjects may be enrolled after device implant**

### Clinical Investigational Plan

## 6.2 STUDY VISITS

The clinical study will be conducted in accordance with the CIP. All parties participating in the conduct of the clinical study will be qualified by education, training, or experience to perform their tasks and this training will be documented appropriately.

The clinical study will not commence until St. Jude Medical receives written approval from the EC or IRB and relevant regulatory authorities and all required documents have been collected from the site(s).

Table 1: List of all study specific activities/procedures

Visit Study Activity	Enrollment Baseline	Implant	Initial Programming site standard of care – Omnidirectional (Day 0)***	3 Month 3 months $\pm$ 30 days since Initial Programming – Directional	6 Month 6 months $\pm$ 30 days since Initial Programming	12 Month 12 months $\pm$ 60 days since Initial Programming	24 Month 24 months $\pm$ 90 days since Initial Programming	36 Month 36 months $\pm$ 90 days since Initial Programming
Inclusion/Exclusion Criteria check	X							
Informed Consent Process	X							
Subject Demographics	X							
Parkinson's Disease History	X							
Parkinson's Disease Medication Current	X					X		X
UPDRS Section II and III Off Medication	X							
UPDRS Section II and III On Medication	X							
UPDRS Section II (On Med On Stim)				X	X	X		X
UPDRS Section III (Off Medication / On Stim)				X*		X		X
UPDRS Section III (Off Medication / Off Stim)				X*		X		X
UPDRS Section III (On Med On Stim)				X*	X*	X		X
UPDRS Section III (On Med Off Stim)				X*	X*	X		X
PDQ-39	X			X	X	X		X
Implant Information		X						
Pre- and Post-Operative Image Collected		X						
Initial testing/ programming data/session data			X*					
Subject Preference					X**			
Clinician Preference					X			

Clinical Investigational Plan

Visit Study Activity	Enrollment Baseline	Implant	Initial Programming site standard of care – Omnidirectional (Day 0)**	3 Month 3 months ± 30 days since Initial Programming – Directional	6 Month 6 months ±30 days since Initial Programming	12 Month 12 months ± 60 days since Initial Programming	24 Month 24 months ±90 days since Initial Programming	36 Month 36 months ±90 days since Initial Programming
System Usability Scale (SUS) Subject						X		
System Usability Scale (SUS) Programmer						X		
Device Testing/ Programming data /session data				X*	X	X*		X
Adverse Event Check		(X)	(X)	(X)	(X)	(X)	(X)	(X)
System Revision Check				(X)	(X)	(X)		(X)
Deviation		(X)	(X)	(X)	(X)	(X)	(X)	(X)
Termination/Exit		(X)	(X)	(X)	(X)	(X)	(X)	(X)

\*Blinded Evaluation      \*\* Blinded Subject      (X) if applicable

\*\*\*For subjects implanted with the Infinity DBS System at the time of enrollment, "Day 0" will be the date of consent.

Baseline and implant information may be retrospectively collected from the subject's medical records after enrollment.

**Informed Consent Procedure and Inclusion/Exclusion Criteria:**

Patient's eligibility criteria will be evaluated and informed consent will be obtained at the Baseline/Enrollment visit.

**Subject Demographics:**

Subject's Age, Weight, Height and Gender will be collected at the Baseline visit.

**Parkinson's Disease History:**

Subject's year of symptom onset, year of initial diagnosis, length of diagnosis, subject's impression of worst symptom, will be collected at the Baseline visit.

**Parkinson's Disease Medication:**

Subject's current medications for PD will be collected at the Baseline visit, at the 12-month and 36-month follow-up visits.

**Subject Data:**

Baseline PDQ-39, UPDRS part II ADLs and part III motor examination scores may be collected from the subject's medical record. PDQ-39, UPDRS part II ADLs On Medication/On Stimulation, and UPDRS part III motor examination On Medication and On and Off Stimulation will be collected at 3, 6, 12 and 36 Month Follow-Up visits. UPDRS part III Off Medication will also be collected at 3-, 12-, and 36-month

## Clinical Investigational Plan

follow-up visits. In addition, subject/programmer satisfaction and data device usage will be collected at the 12-Month Follow-Up visit.

### **Unified Parkinson's Disease Rating Scale/Section II and Section III:**

In order to assess the subject's activities of daily living and Parkinson's disease symptoms, Section II and III of the UPDRS questionnaire will be completed at Baseline, 3-, 6-, 12- and 36-Month Follow-Up visits.

The UPDRS is a rating tool to follow the longitudinal course of Parkinson's disease. It is made up of the following sections: I) Mentation (mental status), Behavior, and Mood, II) Activities of Daily Living (ADL), III) Motor sections and IV) Complications of Therapy, which are evaluated by interviewing the patient. All responses are rated on a 0 to 4-point scale where 0 indicates 'none' and 4 indicates 'severe' symptom.

### **Parkinson's Disease Questionnaire:**

In order to assess the subject's quality of Life the PDQ-39 will be completed at Baseline, 3-, 6-, 12- and 36-Month Follow-Up visits. The PDQ-39 is a disease specific instrument designed to measure aspects of health that are relevant to patients with PD, and which may not be included in general health status questionnaires. The PDQ-39 is a self-administered questionnaire, which comprises 39 items addressing eight domains of health that patients consider to be adversely affected by the disease.

### **Implanted System Information:**

Information regarding the implanted system will be collected during the permanent implantation procedure and in case of additional surgery or from the medical records if patient was already implanted with the Infinity System.

### **Programming Interrogation/Data:**

Programming data and parameters, including program impedance, will be collected during initial programming, at the 3-, 6-, 12- and 36-Month Follow-Up visits. Device session data should be sent to the Sponsor.

### **Evaluation of Programming/Device Testing:**

Detailed device testing will be done at the Initial programming, 3-month follow-up visit, 12-month follow-up visit and 36-month follow-up visit.

### **System Usability Scale/SUS:**

In order to assess the subjects and site programmer's use of the system, a System Usability Scale (SUS), a simple, ten-item scale giving a global view of subjective assessments of usability will be completed by the subject and programmer at the 12 Month Follow-Up visit.

### **Adverse Events:**

Please refer to Section 8.0 of this protocol.

## **6.3 ENROLLMENT VISIT**

The following enrollment activities are performed after the subject has been screened and must occur before any study evaluation /visit.

- The principal or delegated investigator is responsible for screening all potential patients to determine patient eligibility for the study.

## Clinical Investigational Plan

- If a patient meets all inclusion criteria and does not meet any of the exclusion criteria, the patient is eligible for the study.
- The patient is enrolled in the study when the patient signed the EC- or IRB-approved consent form.

Site personnel should record enrollment information (name of the study, date of consent and Inclusion/exclusion information) from the hospital records and complete the Enrollment form electronically in a timely manner (preferably within 5 days after enrollment).

Beginning when the patient signs the Patient Informed Consent form, AEs must be reported according to the guidelines mentioned in this CIP.

In case the subject was consented to participate in the study, but does not meet inclusion/exclusion criteria, and was not implanted, the subject should be withdrawn and a withdrawal form must be completed. The patient will resume regular standard of care with the patient's physician. In case the subject was consented to participate in the study and was implanted but does not meet inclusion/exclusion criteria, then this is considered a protocol violation. A protocol deviation form needs to be completed and the Sponsor must be informed. The EC or IRB and Competent Authority, if applicable, should be notified appropriately about any deviations with regard to the violation of inclusion/exclusion criteria.

### 6.4 BASELINE VISIT

The following information will be collected at the baseline visit (baseline data can be collected on the same day as enrollment/informed consent). Baseline information can be retrospectively collected from the subject's medical records after enrollment:

Demographics

Parkinson's disease history and medication

The following may be collected retrospectively from the subject's medical record. The retrospective data should be collected from the most recent assessments completed prior to the implant date but not greater than 12 months prior:

- UPDRS Off and On Medication – Most recently documented UPDRS
- PDQ-39 – Most recently documented PDQ-39

### 6.5 IMPLANT/PROCEDURE

Subjects will be permanently implanted with the Infinity™ neuromodulation system according to standard operating procedures. It is suggested that the neurosurgeon implant the hourglass shaped radiopaque marker facing posterior or toward them during insertion (toward the back of the subject's head) so that contact/segments are easily identifiable. The orientation of the contacts will be collected. In addition, neurosurgeons will be instructed to plan placement to target between contacts 2 and 3. A pre-operative and post-operative image (MRI/CT) will be obtained to capture lead location data. Subjects will receive a patient programmer if the physician does this as part of his standard of care and will be instructed on the use of the system. Subjects will be unaware of their programmed parameters for the first 6 months.

Following system implantation, the stimulator will be activated and programmed by trained personnel in accordance with the physician's and hospital's standard operating procedures.

## Clinical Investigational Plan

The following information will be collected at the Implantation visit (implant information can be retrospectively collected from the subject's medical records if enrollment occurs after implant):

Lead/extension and IPG data  
Pre-operative and post-operative images  
AE and/or protocol deviation (if applicable)

### 6.6 SCHEDULED FOLLOW-UPS

#### Blinded Evaluation

A blinded evaluator will be used in this study to minimize study bias. The blinded evaluator will assess the therapeutic window for each subject at the initial programming, the 3-month visit and at the 12-month visit. The UPDRS part III motor examination for each subject will also be assessed by the blinded evaluator at the 3-month and 6-month visits. This evaluator will not be aware of the subject's programming or device settings. It is recommended that the blinded evaluator assessing the therapeutic window and the UPDRS part III motor examination should be the same person; however, it is not required. In addition, subjects will be unaware of their programmed parameters for the first 6 months.

Subjects are to be instructed not to take medication the night prior to or the morning of the study visit. This is defined as the Off Medication state. Upon taking appropriate medication, subject is considered to be in the On Medication state.

#### Initial Programming (to be completed according to site's standard of care)

The following will be collected:

- Monopolar review
- AE and/or protocol deviation (if applicable).
- Omnidirectional testing – Off Medication (See Evaluation of Programming)
- Initial programming parameters – Sites will program each lead in an omnidirectional configuration to be used for the first 3 months. If omnidirectional stimulation does not provide adequate therapy or is not tolerated by the subject, any other programming is allowed.

Initial programming information can be retrospectively collected from the subject's medical records if enrollment occurs after implant. For these subjects, the omnidirectional testing by the programmer and blinded evaluator will be completed on the date of consent/enrollment.

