## 4.7 INFORMED CONSENT PROCESS

### 4.7.1 General process

Prior to enrolling in the clinical study and conducting study-specific procedures, all subjects will be required to provide informed consent, as required by applicable regulations and the center's EC or IRB. Informed consent must be obtained from each subject prior to any study-related procedures. The consent form must be signed and dated by the subject and by the person obtaining the consent.

The principal investigator or an authorized designee will conduct the informed consent process. This process will include a verbal discussion with the subject on all aspects of the clinical study that are relevant to the subject's decision to participate in the clinical study.

The subject shall be provided with the informed consent form that is written in a language that is understandable to the subject and has been approved by the center's EC or IRB. Failure to obtain informed consent from a subject prior to study enrollment should be reported to St. Jude Medical within 5 working days and to the reviewing center's EC or IRB consistent with the center's EC or IRB reporting requirements.

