### Evaluation of Programming/Device Testing:

Device testing is to be completed with the subject in the Off Medication state.

Subjects are to be instructed not to take their medication the night prior to or the morning of the study visit; or depending on the type of levodopa medication the subject is taking (i.e.; extended release or long acting) the investigator can use clinical judgement to determine an adequate length of time that the subject should be off medication prior to the testing.

**In order to minimize programming bias, each site will have a designated programmer and a designated blinded evaluator during the omnidirectional and directional device testing. The blinded evaluator will be unaware of the specific program changes made to the device parameters during each testing.**

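### Subjects enrolled after implant must be tested Off Medication on the day they consent; unless they already attend Off for routine care, the consent, medication-state and date rules cannot all be met.

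*Combined protocol and SAP*

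**What the plan says.** The protocol enrols both candidates for implant and people who already carry the Infinity system (section 4.5.1). Five places bear on the second group.

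- Section 6.6, Initial Programming, lists "Omnidirectional testing – Off Medication (See Evaluation of Programming" among the items to collect. For subjects enrolled after implant it adds: "For these subjects, the omnidirectional testing by the programmer and blinded evaluator will be completed on the date of consent/enrollment".
- The Table 1 footnote in section 6.2 sets Day 0 for the same group: "For subjects implanted with the Infinity DBS System at the time of enrollment", Day 0 "will be the date of consent".
- Section 6.6, Blinded Evaluation, defines the Off Medication state: "Subjects are to be instructed not to take medication the night prior to or the morning of the study visit".
- Section 6.6, Evaluation of Programming/Device Testing, applies that state to all device testing: "Device testing is to be completed with the subject in the Off Medication state". It repeats the overnight instruction and then, depending on the type of levodopa (extended release or long acting), says that "the investigator can use clinical judgement to determine an adequate length of time that the subject should be off medication prior to the testing".
- Section 4.7.1: "Informed consent must be obtained from each subject prior to any study-related procedures". Section 4.6.2 makes written consent the moment of enrolment, and section 6.3 places the enrolment activities ahead of any study evaluation or visit.

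**The concern.** Each rule is reasonable alone. Together they ask for a test on the consent date in a state that has to be prepared the evening before. For a person who comes in only for the study, the preparation has no purpose other than the study, and it would happen before that person has agreed to take part. Consent would then be sought from someone already Off Medication.

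The protocol itself treats consent failures as serious. Sections 4.7.1 and 7.2 require a failure to obtain consent to be reported within 5 working days, and section 15.1 lists failure to secure consent before investigational activity among the possible reasons for early termination. A site that avoids the problem by moving the test or relaxing the medication state departs knowingly from the plan. Section 7.2 requires prior approval for that and a deviation form. An entire enrolment route should not depend on such a choice.

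**Working it through.** No statistical quantity enters this point. The check is a comparison of dates.

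**Timing for a subject enrolled after implant**

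1. Consent date = Day 0 (Table 1 footnote).
2. Enrolment date = consent date (section 4.6.2), so the two cannot be separated.
3. Date of the omnidirectional test = consent date = Day 0 (section 6.6, Initial Programming).
4. Start of withholding = no later than the night of Day 0 − 1 = Day −1 (section 6.6, Blinded Evaluation and Evaluation of Programming).
5. Withholding therefore starts on Day −1 and consent is given on Day 0. The preparation precedes consent by at least a night.

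**Routes open to a site when the subject is not already Off for another reason**

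| Route | Rule it breaks |
|---|---|
| Instruct overnight withholding, then consent and test on Day 0 | Section 4.7.1, if study-driven withholding counts as a study-related procedure |
| Consent and test on Day 0 without overnight withholding | Section 6.6, definition of the Off Medication state and its use for device testing |
| Consent on Day 0, test on a later date | Section 6.6, Initial Programming, which fixes the test on the consent date |

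**Possible ways out in the text**

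- Testing over several days within one calendar week is allowed in the 3-month visit instructions. Nothing extends this to Day 0.
- Initial programming information may be collected retrospectively for these subjects. The next sentence, however, requires the omnidirectional test with the programmer and blinded evaluator on the consent date, so it is not covered by that allowance.
- Discretion over the off-medication interval depends on levodopa type. The text states no same-day interval.
- Initial programming is to follow the site's standard of care. A subject who attends Off Medication for routine reasons could consent and be tested that day with no study-driven withholding. This route complies, but nothing limits enrolment after implant to such visits.

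**Where Day 0 windows are used**

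- Primary endpoint and first secondary endpoint: windows at 3 months (sections 4.4.1, 4.4.2, 12.1.1). The omnidirectional test is repeated at that visit, so the comparison needs no Day 0 value.
- Second secondary endpoint: UPDRS part III at 3 and 6 months (section 12.1.2.2).
- Masked interim analysis: 3-month windows, and UPDRS at 3 and 6 months (section 12.4).
- Analysis trigger: 66 subjects with a completed 12-month visit and an evaluable 3-month primary endpoint (section 12.12).

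None of these takes a Day 0 window as input.

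**The case against.** Three arguments can be made for the plan as it stands.

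First, the protocol gives the investigator judgement over the off-medication interval. That is true, but the judgement is tied to extended-release or long-acting levodopa. Reading it as a general permission for a same-day interval stretches the text.

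Second, the standard-of-care heading covers subjects who come in Off for routine programming. This stands, and it sets the limit of the point. A reader might infer that pre-consent withholding is the only way any post-implant subject can be tested compliantly; the documents do not support that, because such a subject can comply. They do not say how common this is.

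Third, section 4.7.1 does not name medication withholding as a study-related procedure. That also stands as a matter of wording. The classification is an inference, though a close one: section 6.6 imposes the withholding by instruction, for the study visit.

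A reader might also infer harm to the statistical results, for instance that Day 0 windows of the two enrolment groups will be contrasted under section 12.7. That section plans a subgroup analysis of endpoints within each enrolment subset. It names neither Day 0 windows nor a comparison between the subsets. Nor do the documents show that sites will take different routes; that would be conjecture about conduct.

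**Conclusion.** The contradiction holds for subjects enrolled after implant who do not already attend Off Medication for routine care. For them no reading of sections 4.7.1, 6.2 and 6.6 satisfies every rule, and the passages must be reconciled. What is at stake is the sequence of consent and, secondarily, the medication state or date of the Day 0 omnidirectional window. No hypothesis test and no analysis trigger is affected.

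The conclusion rests on one assumption: that withholding medication on a study instruction counts as a study-related procedure. The number of subjects concerned cannot be given. Enrolment is capped at 350, and the share enrolled after implant is not stated. The point deserves correction because it concerns consent and costs little to resolve, not because it threatens the study's inference.

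**What to change.** Reconcile section 4.7.1, the Table 1 footnote and the three parts of section 6.6 as follows.

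- In section 6.6, Initial Programming, allow the Day 0 omnidirectional test of subjects enrolled after implant to fall on a date after consent, so that any study-driven preparation follows consent.
- In the same place and in the Table 1 footnote, anchor Day 0 for these subjects to the date of that test.
- In the 3-, 6- and 12-month visit headings, replace the alternative anchor on the consent date with the test date. Otherwise the visit windows would be counted from a date that is no longer Day 0. The 24- and 36-month headings carry no consent-date alternative.

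The content of the medication instruction, and any discretion over it, is for the sponsor and investigators to settle.

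The cost is short edits in five places: the Initial Programming text, the footnote and three headings. No endpoint, hypothesis or sample size changes. The downside is that consent and Day 0 testing may need two visits for these subjects.
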